Understanding Social Situations (USS): Training to improve social function in people with psychosis

NCT04557124

November 1, 2023

PROJECT DESCRIPTION

1. Principal Investigator: [name].

Project Title: Understanding Social Situations (USS): Training to improve social function in people with psychosis

2. Purpose: We propose to evaluate the efficacy of Understanding Social Situations (USS), a behavioral training targeting social cognitive skills. The current proposal is to conduct a fully powered, rigorous randomized controlled trial to test the efficacy of USS versus an active control condition. One hundred twenty Veterans with psychotic spectrum disorders (PSD) will be randomized to 2 months of USS or an active control (AC) intervention matched for duration, therapist contact, and mode of delivery. Key social functioning outcomes will be measured using a multi-method approach of self-report, role-play, and experience sampling, conducted pre-intervention, post-intervention, and at 2 month follow-up, with an additional limited assessment at treatment mid-point.

Primary Aim:

Aim 1: Examine the efficacy of USS in improving social functioning.

H1.1: Compared to AC, USS will be associated with greater improvements on the Social Functioning Scale.

Secondary Aims:

Aim 2: Examine the efficacy of USS in changing real-world social behaviors.

H.2.1: Compared to AC, USS will be associated with greater improvements in real-world social behaviors, as measured by ecological momentary assessment (EMA).

Aim 3: Examine efficacy of USS in improving social interaction skills.

H.3.1: Compared to AC, USS will be associated with greater improvements on the UCSD Social Skills Performance Assessment, a performance-based measure of social skills.

Aim 4: Examine durability of USS effects on clinician and self-rated social functioning, real-world social behaviors, and social skills.

H 4.1 Above group differences will be maintained at 2-month follow-up.

Exploratory Aims: Examine mechanisms of USS effects.

- A. Target engagement and validation: examine impact of USS on a measure of USS content learning (USS Skills Test) and relationship between content learning and improvement in social functioning.
- B. Personalization: explore baseline cognitive, treatment dose, symptom clusters and demographic variables as potential moderators of USS efficacy.

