Analysis of Primary Outcome SFS (Aim 1): The primary objective of the analysis is to demonstrate that USS will improve social functioning at the end of training more than active control in participants with PSD and impaired social functioning. The primary outcome (total scores on the SFS) will be assessed prior to initiation of intervention (pre), the training mid-point (mid), the end of training (post) and 2 months following the end of training (FU). Likelihood-based ignorable analysis using a linear mixed model will be used to compare social functioning between groups^{85, 86}. The primary advantage of the repeated measures linear mixed model when compared to commonly used methods such as complete case analysis and single imputation (e.g. last observation carried forward) is its flexibility in handling missing data. This analysis will assume that missing data occurs at random (i.e. MAR, not informative). The inclusion of pre, mid and FU outcome data in the model will assist in meeting this assumption. Furthermore, we will evaluate patterns of missing data as well as determine baseline characteristics that are predictive of dropout. If identified, these characteristics will be included in the model to meet the MAR assumption. The mixed model will include fixed effects for intervention (USS vs. active control), time (mid, post, FU), and the interaction of intervention with time. An additional fixed effect will be included for baseline SFS at pre. An unstructured covariance pattern will be used to accommodate correlation from repeated measures. A linear contrast will be used to estimate intervention group differences and 95% confidence intervals at the post assessment.

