Analysis of Real World Social Behaviors (Aim 2): Ecological momentary assessment (EMA) analyses will be conducted using a multilevel modeling approach⁸⁷. Analyses handle data estimation with a restricted maximum likelihood approach. Data will be organized hierarchically, with within-person/random EMA prompts across the study period nested within people. Random (within-person) coefficients will be estimated for each person at Level 1, while fixed (between-person) coefficients will be estimated at Level 2. Within-person variables will be centered at Level-1 and between-person variables will be grand mean centered at Level-2⁸⁸⁻⁹⁰. We will examine associations between [e.g., attributions] and [e.g., number of interactions] at Level 1, and fit models with fixed [e.g. group, age, gender] main effects at Level 2. We will also examine [L1] and [L2] cross-level interactions.

Analysis of Social Interaction Skills (Aim 3) and Durability (Aim 4): The secondary outcome social interaction skills, assessed by SSPA, will be compared between USS and control using a repeated measures linear mixed model similar to that described in the analysis of the primary outcome. Durability will also be compared between USS and control using the mixed model. For primary and secondary outcomes, linear contrasts will be used to estimate intervention group differences and 95% confidence intervals at the 2-month FU assessment.

Analysis of Mediation (Exploratory Aim A): We will explore content learning (USS Skills Test) as a potential mediator of the relation between intervention and changes in social functioning. Direct and indirect effects will be estimated using a structural equation model. Mediation (i.e. indirect effects) will be tested using the bootstrapping approach⁹¹.

Analysis of Moderation (Exploratory Aim B): Heterogeneity of treatment effects (HTE) for the primary outcomes will be explored in subgroups of participants based on baseline characteristics including cognition, symptom clusters, illness characteristics, medication dose (chlorpromazine equivalents) and demographic variables. These subgroup analyses are aimed at determining whether there is differential effectiveness of the interventions among participant subgroups. Evidence of HTE will be based on tests of interaction within the longitudinal model structure described above.

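### H4.1 is about keeping the post-training difference, but the only durability contrast named is the USS-AC difference at follow-up, which does not show how much was kept

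*Combined protocol and SAP*

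**What the plan says.** Aim 4 (section 2, Purpose, Secondary Aims) is to "Examine durability of USS effects on clinician and self-rated social functioning, real-world social behaviors, and social skills". Its hypothesis, H4.1, reads "Above group differences will be maintained at 2-month follow-up". No margin, retained share or other definition of maintenance is given.

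The Statistical Analysis Plan, under Social Interaction Skills (Aim 3) and Durability (Aim 4), says "Durability will also be compared between USS and control using the mixed model". For the primary and secondary outcomes it then names the contrast: "linear contrasts will be used to estimate intervention group differences and 95% confidence intervals at the 2-month FU assessment".

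The post-training comparison is set out separately, under Analysis of Primary Outcome SFS (Aim 1): "A linear contrast will be used to estimate intervention group differences and 95% confidence intervals at the post assessment". The same section describes the model: "The mixed model will include fixed effects for intervention (USS vs. active control), time (mid, post, FU), and the interaction of intervention with time", with baseline SFS as a covariate and "An unstructured covariance pattern will be used to accommodate correlation from repeated measures".

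No section names a contrast between the post and follow-up group differences, and none says what result would support H4.1.

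**The concern.** Maintenance describes what happens to the group difference between the end of training and follow-up. A follow-up difference above zero fits full retention, and it also fits substantial decay. A follow-up difference whose interval includes zero fits loss, and it also fits an unchanged effect measured imprecisely. The named contrast cannot separate these cases.

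The post and follow-up estimates would both be reported, so a halving would be visible in the point estimates. What the reader would lack is the precision of that change. It depends on the covariance between the two estimates, which the fitted model holds and the two marginal intervals do not show. The intervention-by-time term is not a substitute: it spans mid, post and FU, so a change between mid and post can drive it, and the plan does not assign it to Aim 4.

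At stake is the wording of a named secondary conclusion. A fading effect could be described as durable, or an unchanged one as lost, and the plan gives no agreed basis for choosing.

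**Working it through.** **Inputs from Justification of Sample Size.** SD of total SFS 13.1; difference at post 9 points; two-sided 0.05; power 90%; 1:1 allocation; 46 per group required; 120 randomised to allow up to 20% dropout.

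**Assumptions, not in the documents.** The SD is the same at post and FU. The baseline-outcome correlation *b* is 0.5 to 0.8 and the post-FU correlation *r* is 0.5 to 0.9. Decay to half the benefit (4.5 points) is an illustration.

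**1. The plan's own figure.** The normal approximation gives 45 per group. The noncentral *t* calculation gives 46 (power 90.3% at 46, 89.7% at 45). For dropout, 92 / 0.8 = 115, so 120 is enough; 120 × 0.8 = 96 completers, or 48 per arm. The stated sample size reproduces. It was set for the post contrast only.

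**2. The FU contrast when half the benefit is gone, unadjusted.** SE = 13.1 × √(2/48) = 2.67. The smallest significant difference is 1.986 × 2.674 = 5.3 points, which is 59% of 9. With a true difference of 4.5, noncentral *t* power is 38%. If all 9 points are kept, power is 91.5%, so the contrast still misses about 8.5% of the time.

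**3. The same contrast with the planned baseline-SFS covariate.** The residual SD is 13.1 × √(1 − b²).

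| b | Smallest significant FU difference | P(significant), true FU difference 4.5 |
|---|---|---|
| 0.5 | 4.6 | 49% |
| 0.6 | 4.3 | 55% |
| 0.7 | 3.8 | 65% |
| 0.8 | 3.2 | 79% |

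An observed difference of 4.5 is itself significant once 5.309 × √(1 − b²) falls below 4.5, that is, once b exceeds about 0.53.

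**4. The change contrast, [USS-AC at FU] minus [USS-AC at post].** SE = 2.674 × √(2(1 − r)). If b is the same at post and FU, baseline adjustment leaves this unchanged. In units of the raw variance, each residual variance is 1 − b² and their covariance is r − b², so the variance of the change is 2(1 − b²) − 2(r − b²) = 2(1 − r).

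| r | SE | 95% half-width | 95% CI if 9 is observed at post and 4.5 at FU | Power to detect a true 4.5-point loss | Power to exclude a 4.5-point loss when nothing is lost |
|---|---|---|---|---|---|
| 0.5 | 2.67 | 5.3 | −9.8 to 0.8 | 38% | 39% |
| 0.7 | 2.07 | 4.1 | −8.6 to −0.4 | 58% | 58% |
| 0.8 | 1.69 | 3.4 | −7.9 to −1.1 | 75% | 76% |
| 0.9 | 1.20 | 2.4 | −6.9 to −2.1 | 96% | 96% |

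The fourth column shows why the separate contrasts are not enough. In every row the unadjusted marginal intervals are the same (9 ± 5.3 and 4.5 ± 5.3), yet the evidence of loss runs from inconclusive to clear.

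**The case against.** The strongest reply is that *maintained* can fairly mean *still present*. H1.1 to H3.1 are statements of group differences, and H4.1 can be read as saying that those differences still exist two months later. The FU contrast answers that directly. This stands as a possible reading, but the plan does not choose it. Leaving the choice open lets the meaning be settled after the results are known.

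It can also be said that the plan commits to comparing durability in the mixed model, which contains the needed parameters. That is true, but the sentence names no estimand, and the only contrast that follows is the one at FU. A further reply is that the change contrast will often be inconclusive. That is also true on the figures above, and it argues for reporting an estimate with its interval rather than a pass-fail test.

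Three stronger readings are tempting and are not supported:

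- A reader might infer that the plan declares USS durable whenever the FU contrast is significant, or counts an effect that first appears at FU. No such rule is stated. The plan promises estimates with intervals, and H4.1 refers back to differences already hypothesised.
- A reader might infer that Aim 4 is the only use made of the follow-up phase. The Aim 1 section includes FU data in the primary model and relies on them to support the missing-at-random assumption.
- A reader might infer that the primary result is compromised. The post contrast is fully specified and is not touched by this point.

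**Conclusion.** The point holds as a gap in specification for a secondary aim. The one contrast named for durability shows whether a benefit is present at follow-up; it cannot show how much of the post-training difference was kept. If the true benefit halves from 9 to 4.5 points, that contrast is still significant about 38% of the time on the raw SD, and about 49% to 79% with the planned covariate. These are chances that a halved benefit remains significant, not a prediction that it will be called durable.

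The figures rest on 48 completers per arm, equal SDs at post and FU, and assumed correlations. They apply to SFS; the documents give no SD for SSPA or EMA. Unless the post-FU correlation is near 0.9, the trial cannot reliably exclude loss of half the benefit. The change should be made before the data are analysed.

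**What to change.** In the Durability (Aim 4) section, for SFS and SSPA, and for the EMA outcome from its own model, add:

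> From the same model, estimate [USS-AC at FU] minus [USS-AC at post] with a 95% CI, and report it beside the post and FU contrasts. A significant FU contrast alone will be described as a benefit present at follow-up. Statements about maintenance will rest on the change estimate and its CI, and a non-significant change will not be taken as proof of maintenance.

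For EMA this requires that model to include group, assessment period and their interaction; the Aim 2 text currently leaves its variables as placeholders.

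The cost is one extra estimate statement per outcome and a short addition to the plan, with no new data or visits. The downside is a more guarded durability conclusion, because the interval for the change is several points wide unless post and FU scores are very highly correlated.
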